# Table 5 Response Assessment Criteria for Lymphoma

Response and Site	PET-CT-Based Response	CT-Based Response	
		by >50% of the extent of its prior increase beyond baseline (e.g., a 15-cm spleen must increase to >16 cm). If no prior splenomegaly, must increase by at least 2 cm from baseline New or recurrent splenomegaly	
Nonmeasured lesions	None	New or clear progression of preexisting nonmeasured lesions	
New lesions	New FDG-avid foci consistent with lymphoma rather than	Regrowth of previously resolved lesions	
	another etiology (e.g., infection,	A new node >1.5 cm in any axis	
	inflammation). If uncertain regarding etiology of new lesions, biopsy or interval scan may be considered		
		Assessable disease of any size unequivocally attributable to lymphoma	
Bone marrow	New or recurrent FDG-avid foci	New or recurrent involvement	

#### Table 5 Response Assessment Criteria for Lymphoma

#### Cheson 2014.

5PS=5-point scale; CT=computed tomography; FDG=fluorodeoxyglucose; GI=gastrointestinal;

IHC=immunohistochemistry; LDi=longest transverse diameter of a lesion; MRI=magnetic resonance imaging; PET=positron emission tomography; PPD=cross product of the LDi and perpendicular diameter; SDi=shortest axis perpendicular to the LDi; SPD=sum of the product of the perpendicular diameters for multiple lesions.

\*A score of 3 in many patients indicates a good prognosis with standard treatment, especially if at the time of an interim scan. However, in trials involving PET where de-escalation is investigated, it may be preferable to consider a score of 3 as inadequate response (to avoid undertreatment). Measured dominant lesions: Up to six of the largest dominant nodes, nodal masses, and extranodal lesions selected to be clearly measurable in two diameters. Nodes should preferably be from disparate regions of the body and should include, where applicable, mediastinal and retroperitoneal areas. Non-nodal lesions include those in solid organs (e.g., liver, spleen, kidneys, lungs), GI involvement, cutaneous lesions, or those noted on palpation. Nonmeasured lesions: Any disease not selected as measured, dominant disease and truly assessable disease should be considered not measured. These sites include any nodes, nodal masses, and extranodal sites not selected as dominant or measurable or that do not meet the requirements for measurability but are still considered abnormal, as well as truly assessable disease, which is any site of suspected disease that would be difficult to follow quantitatively with measurement, including pleural effusions, ascites, bone lesions, leptomeningeal disease, abdominal masses, and other lesions that cannot be confirmed and followed by imaging. In Waldeyer's ring or in extranodal sites (e.g., GI tract, liver, bone marrow), FDG uptake may be greater than in the mediastinum with complete metabolic response, but should be no higher than surrounding normal physiologic uptake (e.g., with marrow activation as a result of chemotherapy or myeloid growth factors).

+PET 5PS: 1) No uptake above background; 2) Uptake ≤ mediastinum; 3) Uptake > mediastinum but ≤ liver; 4) Uptake moderately > liver; 5) Uptake markedly higher than liver and/or new lesions; X) New areas of uptake unlikely to be related to lymphoma.

Table 6 Res	ponse Assessment Criteria for CLL/SLL
-------------	---------------------------------------

Response	Lymphocytes	Bone Marrow	Physical Examination b (Nodes, Liver, Spleen)	Peripheral Blood
CR ª	Lymphocytes <4×10  /L	Normocellular <30% lymphocytes No B-lymphoid nodules	Normal (e.g., no lymph nodes >1.5 cm)	ANC >1.5×10  /L c Platelets >100×10  /L c Hemoglobin >11.0 g/dL (untransfused) b
CRi	Lymphocytes <4×10  /L	Hypocellular <30% lymphocytes	Normal (e.g., no lymph nodes >1.5 cm)	Persistent anemia, thrombocytopenia, or neutropenia related to drug toxicity
nPR	CR with the	presence of lymphoid no	odules in the bone marrow which reflect	residual disease
PRª	Lymphocytes <5×10  /L Or ≥50% decrease from baseline	Not assessed	≥50% reduction in lymphadenopathy d and/or in spleen or liver enlargement	ANC >1.5×10  /L Or Platelets >100×10  /L or ≥50% improvement over baseline b Or Hemoglobin >11.0 g/dL or ≥50% improvement over baseline (untransfused)°
PRL a	Lymphocytes ≥5×10  /L And <50% decrease from baseline	Not assessed	≥50% reduction in lymphadenopathy d and/or in spleen or liver enlargement	ANC >1.5×10  /L Or Platelets >100×10  /L or ≥50% improvement over baseline ° Or Hemoglobin >11.0 g/dL or ≥50% improvement over baseline (untransfused) °

#### Table 6 Response Assessment Criteria for CLL/SLL

Response	Lymphocytes	Bone Marrow	Physical Examination b (Nodes, Liver, Spleen)	Peripheral Blood
SD	Absence of PD and failure to achieve at least a PR			
PDª	Lymphocytes ≥50% increase over baseline	Not assessed (except to confirm PD as assessed by progressive cytopenias)	Appearance of any new lesion or de novo appearance of hepatomegaly or splenomegaly Or Increase ≥50% in lymphadenopathy Or Increase ≥50% in hepatomegaly Or Increase ≥50% in splenomegaly	Platelets decrease of ≥50% from baseline secondary to CLL or <100,000 µL and worsening bone marrow due to CLL Or Hemoglobin decrease of >2 g/dL from baseline secondary to CLL or decrease to <100 g/L and worsening bone marrow due to CLL

#### Modified From Hallek 2008.

ANC=absolute neutrophil count; CLL= chronic lymphocytic leukemia; CR=complete remission (response); CRi=CR with incomplete bone marrow recovery; nPR=nodular partial response; PD=progressive disease; PR=partial remission (response); PRL=partial remission (response) with lymphocytosis; SD=stable disease.

- a CR: all of the above CR criteria have to be met, and patients have to lack disease-related constitutional symptoms; PR: at least two of the above PR criteria for lymphadenopathy, splenomegaly, hepatomegaly, or lymphocytes plus one of the criteria for ANC, platelets or hemoglobin have to be met; PRL: presence of lymphocytosis, plus ≥50% reduction in lymphadenopathy and/or in spleen or liver enlargement, plus one of the criteria for ANC, platelets or hemoglobin have to be met; PD: at least one of the above PD criteria has to be met or transformation to a more aggressive histology (e.g., Richter's syndrome). For PD as assessed by progressive cytopenias, a bone marrow biopsy is required for confirmation. Note: Isolated elevation of treatment-related lymphocytosis by itself will not be considered PD unless patient becomes symptomatic from this per Cheson 2012.
- b Computed tomography (CT) scan of abdomen, pelvis, and thorax may be used if previously abnormal.
- c Without need for exogenous growth factors.
- d In the sum products of ≤6 lymph nodes or in the largest diameter of the enlarged lymph node(s) detected before therapy and no increase in any lymph node or new enlarged lymph nodes.

Table 7	Response Assessment Criteria for WM
---------	-------------------------------------

Response	Definition
Complete response (CR)	
 
Absence of serum monoclonal IgM protein by immunofixation
 
Normal serum IgM level
 
Complete resolution of extramedullary disease, i.e., lymphadenopathy and splenomegaly if present at baseline
 
Morphologically normal bone marrow aspirate and trephine biopsy
 

Very good partial response (VGPR)	
 
Monoclonal IgM protein is detectable
 
≥90% reduction in serum IgM level from baseline a
 
Complete resolution of extramedullary disease i.e., lymphadenopathy/splenomegaly if present at baseline
 
No new signs or symptoms of active disease
 

Partial response (PR)	
 
Monoclonal IgM protein is detectable
 
≥50% but <90% reduction in serum monoclonal IgM level from baseline a
 
Reduction in extramedullary disease i.e., lymphadenopathy/splenomegaly if present at baseline
 
No new signs for symptoms of active disease
 

Minor response (MR)	
 
Monoclonal IgM protein is detectable
 
≥25% but <50% reduction in serum monoclonal IgM level from baseline a
 
No new signs for symptoms of active disease
 

Stable disease (SD)	
 
Monoclonal IgM protein is detectable
 
<25% reduction and <25% increase in serum monoclonal IgM level from baseline*
 
No progression in extramedullary disease i.e., lymphadenopathy/splenomegaly
 
No new signs for symptoms of active disease
 

Progressive disease	
 
≥25% increase in serum IgM level a from lowest nadir (requires confirmation on ≥2 consecutive measurements at least 4 weeks apart).
 
AND
 
Progression of clinical features attributable to the disease per Owen 2013.
 

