### 4.2 INVESTIGATOR'S ASSESSMENT OF RESPONSE TO TREATMENT

The investigator must rate the response of the subjects as outlined below:

- NHL, Hodgkin lymphoma, or RS refer to Table 5
- CLL/SLL refer to Table 6
- WM refer to Table 7
- MM refer to Table 8
- MF refer to Table 9

Response and Site	PET-CT-Based Response	CT-Based Response	
Complete	Complete metabolic response Complete radiologic resp (all of the following)		
lymphatic sites a residual mass on 5PS+ must regress to ≤1		Target nodes/nodal masses must regress to ≤1.5 cm in LDi No extralymphatic sites of disease	
Nonmeasured lesion	Not applicable	Absent	
Organ enlargement	Not applicable	Regress to normal	
New lesions	None	None	
Bone marrow	No evidence of FDG-avid disease in the marrow	Normal by morphology; if indeterminate, IHC negative	
Partial	Partial metabolic response	Partial remission (all of the following)	
Lymph nodes and extra lymphatic sites	Score 4 or 5+ with reduced uptake compared with baseline and residual mass(es) of any size At interim, these findings suggest responding disease	
 
≥50% decrease in SPD of up to 6 target measurable nodes and extranodal sites
 
When a lesion is too small to measure on CT, assign
 
	
	At end of treatment, these findings indicate residual disease	5 mm×5 mm as the default value When no longer visible, 0 mm×0 mm For a node >5 mm×5 mm, but smaller than the normal, use actual measurement for calculation	
Nonmeasured lesions	Not applicable	Absent/normal, regressed, but no increase	

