12.3 Censoring Rules for Progression-free Survival

Situation	Outcome	Date	Event Description/ Censoring Reason
Progression documented between scheduled visits on or before receiving subsequent anticancer therapy or data cutoff, whichever occurred first	Event	Earliest date of disease assessment documenting progression	PD
Death without documented PD on or before receiving subsequent anti-cancer therapy or data cutoff, whichever occurred first	Event	Date of Death	Death
death before first adequate disease assessment	Event	Date of Death	Death
New anti-cancer treatment Started before PD or death for subjects with or without documented PD or death and before data cutoff	Censored	Date of last adequate disease assessment prior to subsequent anti-cancer treatment	New anti-cancer Therapy
No documented PD or death at the time of data cutoff and subject not received subsequent anti-cancer therapy or subsequent anti-cancer therapy start date after the data cutoff	Censored	Date of last adequate disease assessment on or before data cutoff	Data cutoff
Withdrew consent before documented PD or death	Censored	Date of last adequate disease assessment	Withdrew consent
Lost to follow-up before documented PD or death	Censored	Date of last adequate disease assessment	Lost to follow-up
No post-baseline adequate disease assessments	Censored	Date of first dose	No post-baseline adequate disease assessments
No baseline disease assessments	Censored	Date of first dose	No baseline disease assessment

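### Waldenström progression in Table 7 needs both an IgM rise and clinical progression, so single-limb progression is never scored PD and the descriptive WM PFS and DOR are biased upward

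*Protocol*

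**What the plan says.** Protocol Section 4.2 has the investigator rate response by disease-specific tables, and for this disease the instruction is "WM refer to Table 7".

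- **PD row.** The first limb is an IgM rise of at least 25% "from lowest nadir (requires confirmation on ≥2 consecutive measurements at least 4 weeks apart". The second is clinical progression, defined only by reference to the cited WM criteria. A stand-alone AND joins them: "at least 4 weeks apart). AND Progression of clinical features attributable to the disease".
- **SD row.** Three conditions apply together. The rise must be less than a "25% increase in serum monoclonal IgM level from baseline" (with a matching limit on reduction). There must also be "No progression in extramedullary disease i.e., lymphadenopathy/splenomegaly" and "No new signs for symptoms of active disease".
- **PR and MR rows.** IgM is again counted from baseline, and new signs or symptoms are excluded. PR also needs a reduction in any extramedullary disease present at baseline. MR has no extramedullary condition.

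The SAP defers to Protocol Section 4.2 for response and counts MR or better as a WM response (9.6.1.1). SAP 12.2 and 12.3 date a progression event at the "Earliest date of disease assessment documenting progression" and also count death. Starting new therapy before PD or death censors the subject at the last adequate assessment before it. Neither table has a rule for an assessment that is neither SD nor PD.

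**The concern.** The SD and PD rows do not meet. SD treats either limb alone as disqualifying, while PD treats neither alone as sufficient. They also use different reference points, baseline for SD and nadir for PD. Both features are visible in the table itself, whatever the cited criteria say.

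Table 7 also differs from its neighbours. Tables 5, 6 and 8 call progression on any one listed criterion, apart from an exception in Table 6 for isolated treatment-related lymphocytosis. SD is a residual category in Tables 6 and 8, so this gap cannot arise there.

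WM PFS and DOR are at stake. SAP 9.1 presents WM as its own group in the same summary tables as the other diseases, so its figures would rest on a stricter progression rule than those beside it.

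**Working it through.** The plan states no figure on this point, so there is none to reproduce. The check applies each row of Table 7 to subjects who have exactly one limb of progression. IgM is written as a ratio to baseline. The clinical limb is taken as extramedullary progression or new signs or symptoms, which is an assumption because the table defines it only by citation. IgM rises of 25% or more are taken as confirmed. The values are illustrative.

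| Case | IgM / baseline | Rise from nadir | Clinical limb | Row met |
|---|---|---|---|---|
| Non-responder, IgM only | 1.25, 1.5, 2.0 | 25%, 50%, 100% | absent | none |
| Non-responder, clinical only | 0.9, 1.0, 1.2 | 0%, 0%, 20% | present | none |
| Responder, IgM only | 0.75 to 0.94 | 25% | absent | SD |
| Responder, IgM only | 0.50 to 0.75 | 50% | absent | MR |
| Responder, IgM only | 0.10 to 0.30 | 200% | absent | PR, if extramedullary disease is reduced |
| Responder, clinical only (nodes, no new signs or symptoms) | 0.70 | 0% | present | MR |
| Responder, clinical only (new signs or symptoms) | 0.70, 0.50, 0.30, 0.10 | 0% | present | none |

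**A worked responder.** IgM goes from 40 g/L at baseline to a nadir of 10 and then to 20.
- Rise from nadir: 20/10 − 1 = 100%, so the IgM limb is met.
- Change from baseline: 20/40 − 1 = −50%, which is in the PR range.
- With no clinical progression the subject stays PR, provided any baseline extramedullary disease remains reduced.

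**How far IgM can climb first.** On IgM alone, a responder leaves SD upward only at 1.25 times baseline. The rise from nadir needed is 1.25/nadir − 1:
- nadir 0.75: 1.25/0.75 − 1 = 67%
- nadir 0.50: 1.25/0.50 − 1 = 150%
- nadir 0.10: 1.25/0.10 − 1 = 1150%

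Even then the subject leaves SD for no row, not for PD.

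**Effect on the endpoints.** PD is recorded in none of these cases. Under SAP 12.2 and 12.3 there are three ways forward:
- the second limb appears, and the event is dated then;
- the subject dies first, and the event is dated at death;
- new therapy starts first, and the subject is censored.

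The first two lengthen the recorded time. The third replaces a progression with a censored observation. All three push WM PFS and DOR upward.

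**The case against.** The strongest objection is that the PD row points to published WM criteria that are not in the documents. The AND may be the source rule or a deliberate choice. This stands: a reader might infer that AND is a slip for OR, and the documents cannot show that. It does not remove the conflict between the SD and PD rows.

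A reader might also infer that every single-limb progressor has no category and that all their events are missed. The documents do not support this. Some responders still meet SD, MR or PR, and death remains an event. Events are delayed, or lost to censoring, rather than always missed.

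Changing one word in the table might look like a complete repair. It is not. A subject going from 40 to 10 to 20 g/L would then meet both PR and PD, and an unconfirmed rise of 25% or more above baseline would still be neither SD nor PD. Because Sections 3.0 and 3.6 tie coming off treatment to confirmed progression, rewriting the PD row would also alter a treatment trigger.

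The contrast with other tables has limits. Table 6 does not count isolated treatment-related lymphocytosis as PD unless the subject becomes symptomatic, and Table 9 requires imaging confirmation of splenic progression. No comparison between diseases is planned, and SAP Section 5 specifies no formal hypothesis test. On treatment, Section 3.6 provides for uncertain progression and Section 3.11 allows withdrawal at the investigator's decision. These points limit the importance of the finding but leave the bias in place.

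**Conclusion.** The defect holds in this form: if Table 7 is followed as written, no single-limb WM progression is scored PD at the assessment where it appears, and WM PFS and DOR are biased upward. This rests on reading the AND literally and on investigators applying the rows as printed.

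The size cannot be computed. Part 2 allows up to 30 subjects per histology, but that is a cap. WM enrollment stopped under Amendment 3, and the study closed with 161 evaluable subjects in all, with no WM count given. The share of progressions showing one limb first is not given either. A reader might infer that most events are affected because two of the three patterns (IgM only, clinical only, both) escape PD. That counts logical cases, not their frequency.

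The effect is confined to two descriptive secondary endpoints in one disease group. It should be corrected, but it does not threaten the study's main conclusions.

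**What to change.** **Protocol.** The sponsor must reconcile the PD and SD rows of Table 7 with each other, with the cited WM criteria, and with the wording on confirmed progression in Sections 3.0 and 3.6. No stopping rule is proposed here.

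**SAP 9.6.2, 9.6.3, 12.2 and 12.3, for endpoint scoring only.** Derive WM PFS and DOR with the event at the first of the two limbs, either a confirmed IgM rise of 25% or more from nadir or clinical progression. State that PD takes precedence over any PR, MR or SD row also met. State whether a confirmed IgM rise is dated at the first raised value or at the confirming one, and how an unconfirmed rise is handled. Present the both-limb version alongside, so that nothing is lost if the AND is intended.

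**Cost.** One extra derivation for one disease group. No new assessments are needed, because disease markers, serum immunoglobulin, physical examinations and imaging are already scheduled in Protocol Appendix 5. WM PFS and DOR would become somewhat shorter. SAP Section 1 already provides for changes of method to be documented in the clinical study report.

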#### Owen 2013.

IgM=immunoglobulin M; WM=Waldenström macroglobulinemia.

a Sequential changes in IgM levels may be determined either by M protein quantitation or total serum IgM quantitation by nephelometry.

Response Subcategory	Response Criteria a	
Complete response (CR)	
 
Negative immunofixation on the serum and urine and
 
	
	Disappearance of any soft tissue plasmacytomas and	
	
 
<5% plasma cells in bone marrowb.
 
	
Stringent complete response (sCR)	CR as defined above plus	
response (SCR)	Normal FLC ratio and	
	Absence of clonal cells in bone marrow b by immunohistochemistry or immunofluorescence c .	
Near complete response (nCR)	
 
Meeting the criteria for CR, except that the persistence of original monoclonal protein by immunofixation while absence of monoclonal protein on serum or urine protein electrophoresis.
 
	
Very good partial response (VGPR)	
 
Serum and urine M-component detectable by immunofixation but not on electrophoresis or
 
	
	
 
≥90% reduction in serum M-component plus urine M-component
 
<100 mg/24 h.
 
	
Partial response (PR)	
 
≥50% reduction of serum M-protein and reduction in 24-h urinary M-protein by ≥90% or to <200 mg/24 h
 
	
	
 
If the serum and urine M-protein are unmeasurable at baseline, a ≥50% decrease in the difference between involved and uninvolved FLC levels is required in place of the M-protein criteria
 
	
	
 
If serum and urine M-protein are unmeasurable at baseline, and serum free light assay is also unmeasurable, ≥50% reduction in plasma cells is required in place of M-protein, provided baseline bone marrow plasma cell percentage was ≥30%
 
	
	
 
In addition to the above listed criteria, if present at baseline, a ≥50% reduction in the size of soft tissue plasmacytomas is also required
 
	
Minor response (MR)	• MR includes subjects in whom some, but not all, criteria for PR are fulfilled providing the remaining criteria satisfy the requirements for MR.	
	
 
Requires all of the following:         
 
≥25% to ≤49% reduction in the level of serum monoclonal protein for ≥2 determinations 6 weeks apart.
 
If present, a 50% to 89% reduction in 24-hour light chain excretion, which still exceeds 200 mg/24 h, for ≥2 determinations 6 weeks apart.
 
25% to 49% reduction in the size of plasmacytomas (by clinical or radiographic examination) for ≥6 weeks.
 
No increase in size or number of lytic bone lesions
 
 
 
	
	(development of compression fracture does not exclude response).	
Stable disease - SD (not recommended for use as an indicator of response; stability of disease is best described by providing the	
 
Not meeting criteria for CR, VGPR, MR, PR or progressive disease
 
	

# Table 8 Response Criteria for MM (incorporating EBMT and IMWG)

Response Subcategory	Response Criteria a
time to progression estimates)	
Progression Subcategory	Progression Criteria d
Progressive disease a — To be used for calculation	Laboratory or biochemical relapse or progressive disease: requires the occurrence of ≥1 of any of the following:
of duration of response and progression-free	
 
Increase of ≥25% from lowest response value in serum M- component and/or (the absolute increase must be ≥0.5 g/dL)e.
 

survival end points for all subjects including those in CR (includes primary	
 
Urine M-component and/or (the absolute increase must be ≥200 mg/24 h).
 

progressive disease and disease progression on or off therapy) g	
 
Only in subjects without measurable serum and urine M-protein levels: the difference between involved and uninvolved FLC levels. The absolute increase must be >10 mg/dL.
 

	
 
Bone marrow plasma cell percentage: the absolute % must be ≥10%f.
 

	
 
Definite development of new bone lesions or soft tissue plasmacytomas or definite increase in the size of existing bone lesions or soft tissue plasmacytomas.
 

#### Table 8Response Criteria for MM (incorporating EBMT and IMWG)

EBMT: Bladé 1998; IMWG: Durie 2006.

EBMT=European Group for Blood and Marrow Transplant; FLC=(serum) free light chains; IMWG=International Myeloma Working Group; MM=multiple myeloma.

Note: \* Note clarification to IMWG criteria for coding CR and VGPR in subjects in whom the only measurable disease is by serum FLC levels: CR in such subjects a normal FLC ratio of 0.26-1.65 in addition to CR criteria listed above. VGPR in such subjects is defined as a >90% decrease in the difference between involved and uninvolved free light chain FLC levels

- a. All response categories require 2 consecutive assessments made at ≥4 weeks after the start of study therapy and any time before the institution of any new therapy after study therapy; CR and PR and SD categories also require no known evidence of progressive or new bone lesions if radiographic studies were performed. Radiographic studies are not required to satisfy these response requirements.
- b. Confirmation with repeat bone marrow biopsy not needed
- c. Presence/absence of clonal cells is based upon the kappa/lambda ratio. An abnormal kappa/lambda ratio by immunohistochemistry and/or immunofluorescence requires a minimum of 100 plasma cells for analysis. An abnormal ratio reflecting presence of an abnormal clone is kappa/lambda of >4:1 or <1:2.
- d. All relapse categories require 2 consecutive assessments made at any time before classification as relapse or disease progression and/or the institution of any new therapy.
- e. For progressive disease, serum M-component increases of ≥1 gm/dL are sufficient to define relapse if starting M-component is ≥5 g/dL.
- f. Relapse from CR has the 5% cutoff versus 10% for other categories of relapse.
- g. For purposes of calculating time to progression and progression-free survival, CR subjects should also be evaluated using criteria listed above for progressive disease.

Response Categories	Required Criteria (for all response categories, benefit must last for ≥12 weeks to qualify as a response)
Complete response (CR)	
 
Bone marrow:* Age-adjusted normocellularity; <5% blasts; Grade ≤1 MF† and
 
Peripheral blood: Hemoglobin ≥100 g/L and <unl; count="" neutrophil="" ≥1×109/L and <unl;< li=""> 
Platelet count ≥100×10^9/L and <unl; <2%="" and<="" cells‡="" immature="" li="" myeloid=""> 
Clinical: Resolution of disease symptoms; spleen and liver not palpable; no evidence of EMH
 </unl;>
</unl;<></unl;>

Partial response (PR)	
 
Peripheral blood: Hemoglobin ≥100 g/L and <unl; count="" neutrophil="" ≥1×109/L and <unl; count="" platelet="" ≥100×109/L and <unl; <2%="" and<="" cells‡="" immature="" li="" myeloid=""> 
Clinical: Resolution of disease symptoms; spleen and liver not palpable; no evidence of EMH or
 
Bone marrow:* Age-adjusted normocellularity; <5% blasts; Grade <1 MF†, and peripheral blood: Hemoglobin ≥85 but <100 g/L and <unl; count="" neutrophil="" ≥1×109/L and <unl; <100×109/L and <unl; <2%="" and<="" cells‡="" immature="" li="" myeloid=""> 
Clinical: Resolution of disease symptoms; spleen and liver not palpable; no evidence of EMH
 </unl;></unl;></unl;>
</unl;></unl;></unl;>

Clinical improvement (CI)	
 
The achievement of anemia, spleen or symptoms response without progressive disease or increase in severity of anemia, thrombocytopenia, or neutropenia§
 

Anemia response	
 
Transfusion-independent patients: a ≥20 g/L increase in hemoglobin level
 
Transfusion-dependent patients: becoming transfusion-independent
 

Spleen response	
 
A baseline splenomegaly that is palpable at 5 to 10 cm, below the LCM, becomes not palpable# or
 
A baseline splenomegaly that is palpable at >10 cm, below the LCM, decreases by ≤50%#
 
A baseline splenomegaly that is palpable at <5 cm, below the LCM, is not eligible for spleen response
 
A spleen response requires confirmation by MRI or computed tomography showing ≥35% spleen volume reduction**
 

Symptoms response	
 
A ≥50% reduction in the MPN-SAF TSS††
 

Response Categories	Required Criteria (for all response categories, benefit must last for ≥12 weeks to qualify as a response)
Progressive disease	
 
Appearance of a new splenomegaly that is palpable at least 5 cm below the LCM or‡‡
 
A ≥100% increase in palpable distance, below LCM, for baseline splenomegaly of 5-10 cm or‡‡
 
A 50% increase in palpable distance, below LCM, for baseline splenomegaly of >10 cm or‡‡
 
Leukemic transformation confirmed by a bone marrow blast count of ≥20% or
 
A peripheral blood blast content of ≥20% associated with an absolute blast count of ≥1×10^9/L that lasts for at least 2 weeks
 

Stable disease	Belonging to none of the above listed response categories
Relapse	
 
No longer meeting criteria for at least CI after achieving CR, PR, or CI, or
 
Loss of anemia response persisting for at least 1 month or
 
Loss of spleen response persisting for at least 1 month
 

Recomme	ndations for assessing treatment-induced cytogenetic and molecular changes
Cytogenetic remission	
 
At least 10 metaphases must be analyzed for cytogenetic response evaluation and
 
requires confirmation by repeat testing within 6 months window
 
CR: eradication of a pre-existing abnormality
 
PR: ≥50% reduction in abnormal metaphases
 
(partial response applies only to patients with at least ten abnormal metaphases at baseline)
 

Molecular remission	
 
Molecular response evaluation must be analyzed in peripheral blood granulocytes and
 
requires confirmation by repeat testing within 6 months window
 
CR: Eradication of a pre-existing abnormality
 
PR: ≥50% decrease in allele burden
 
(partial response applies only to patients with at least 20% mutant allele burden at baseline)
 

Cytogenetic/ molecular relapse	Re-emergence of a pre-existing cytogenetic or molecular abnormality that is confirmed by repeat testing

Tefferi 2013.

EMH=extramedullary hematopoiesis (no evidence of EMH implies the absence of pathology- or imaging study-proven nonhepatosplenic EMH); LCM=left costal margin; UNL=upper normal limit.

- \* Baseline and posttreatment bone marrow slides are to be interpreted at one sitting by a central review process. Cytogenetic and molecular responses are not required for CR assignment.
- † Grading of MF is according to the European classification

Thiele et al. European consensus on grading bone marrow fibrosis and assessment of cellularity. Haematologica. 2005;90:1128.

It is underscored that the consensus definition of a CR bone marrow is to be used only in those patients in which all other criteria are met, including resolution of leukoerythroblastosis.

It should also be noted that it was a particularly difficult task for the working group to reach a consensus regarding what represents a complete histologic remission.

- Immature myeloid cells constitute blasts + promyelocytes + myelocytes + metamyelocytes + nucleated red blood cells. In splenectomized patients, <5% immature myeloid cells is allowed.

- § See above for definitions of anemia response, spleen response, and progressive disease. Increase in severity of anemia constitutes the occurrence of new transfusion dependency or a ≥20 g/L decrease in hemoglobin level from pretreatment baseline that lasts for at least 12 weeks. Increase in severity of thrombocytopenia or neutropenia is defined as a 2-grade decline, from pretreatment baseline, in platelet count or absolute neutrophil count, according to the Common Terminology Criteria for Adverse Events (CTCAE) version 4.0. In addition, assignment to CI requires a minimum platelet count of ≥25 000×10^9/L and absolute neutrophil count of ≥0.5×10^9/L.
- || Applicable only to patients with baseline hemoglobin of <100 g/L. In patients not meeting the strict criteria for transfusion dependency at the time of study enrollment (see as follows), but have received transfusions within the previous month, the pretransfusion hemoglobin level should be used as the baseline.
- { Transfusion dependency before study enrollment is defined as transfusions of at least 6 units of packed red blood cells (PRBC), in the 12 weeks prior to study enrollment, for a hemoglobin level of <85 g/L, in the absence of bleeding or treatment-induced anemia. In addition, the most recent transfusion episode must have occurred in the 28 days prior to study enrollment. Response in transfusion-dependent patients requires absence of any PRBC transfusions during any consecutive "rolling" 12-week interval during the treatment phase, capped by a hemoglobin level of ≥85 g/L.
- # In splenectomized patients, palpable hepatomegaly is substituted with the same measurement strategy.
- \*\* Spleen or liver responses must be confirmed by imaging studies where a ≥35% reduction in spleen volume, as assessed by MRI or CT, is required. Furthermore, a ≥35% volume reduction in the spleen or liver, by MRI or CT, constitutes a response regardless of what is reported with physical examination.
- ++ Symptoms are evaluated by the MPN-SAF TSS (Emanuel 2012). The MPN-SAF TSS is assessed by the patients themselves and this includes fatigue, concentration, early satiety, inactivity, night sweats, itching, bone pain, abdominal discomfort, weight loss, and fevers. Scoring is from 0 (absent/as good as it can be) to 10 (worst imaginable/as bad as it can be) for each item. The MPN-SAF TSS is the summation of all the individual scores (0-100 scale). Symptoms response requires ≥50% reduction in the MPN-SAF TSS.
- ‡‡ Progressive disease assignment for splenomegaly requires confirmation my MRI or computed tomography showing a ≥25% increase in spleen volume from baseline.
- Baseline values for both physical examination and imaging studies refer to pretreatment baseline and not to posttreatment measurements.

